3.1 Demographics and Baseline Characteristics

Descriptive statistics for demographics and baseline characteristics will be presented by randomized treatment group for participants enrolled on BMT CTN 0702 and separately for participants enrolled on BMT CTN 07LT.

Testing of treatment group differences among all participants enrolled on BMT CTN 0702 will be conducted to determine which characteristics to include the in the Cox regression model for PFS. Factors with a significance level <0.1 based on a chi-square test of differences using all three treatment arms (not pairwise tested) will be included in the Cox regression model. Factors to be summarized include, but are not limited to, those listed below. Factors to be considered for inclusion in the Cox regression model and tested for treatment group differences are limited to those marked in the second column below.

For the factor of ERC-adjudicated disease response at study entry, 2 categorizations will be considered: CR or greater vs less than CR, and VGPR or greater vs less than VGPR.

Factors for descriptive summary statistics	Factors to consider for inclusion in Cox model
Baseline data from 0702 randomization	
Baseline disease risk strata (as randomized)	Will be included even if no difference
	among treatment groups
Baseline disease risk strata (updated post randomization)	Will not be included
Gender	Will be considered for inclusion
Ethnicity	Will be considered for inclusion
Race	Will be considered for inclusion
Karnofsky performance score	Will be considered for inclusion
ERC-adjudicated disease response at BMT CTN 0702 study	Will be considered for inclusion
entry	
Age at 0702 enrollment	Will be considered for inclusion
Pre-0702 initial therapy for myeloma (doublets/triplets/other)	Will be considered for inclusion

Factors for descriptive summary statistics	Factors to consider for inclusion in Cox model
Baseline data for those enrolled on 07LT	
Baseline disease risk strata (as randomized)	Will not be included
Gender	Will not be included
Ethnicity	Will not be included
Race	Will not be included
Karnofsky performance score	Will not be included
ERC-adjudicated disease response at BMT CTN 0702 study	Will not be included
entry	
Age at 07LT enrollment	Will not be included

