#### 5.3. Analysis of the Primary Endpoint

The primary analysis will include all randomized subjects from the BMT CTN 0702 protocol, classified according to their randomized treatment allocation, irrespective of treatment actually received [intent-to-treat]. The time to this event is the time from randomization on the BMT CTN 0702 protocol to progression, initiation of non-protocol anti-myeloma therapy, or death from any cause. Patients will be censored at loss to follow-up or end of 2018, whichever comes first. Deaths without progression are treated as failures no matter when they occur. The analysis will be conducted once all living patients have been followed for 5-years post randomization on the BMT CTN 0702 protocol.

Data for patients not enrolled on the long-term follow-up protocol will be included from the BMT CTN 0702 protocol. Additionally, patients who do not consent to the long-term follow-up or who have progressed on the BMT CTN 0702 protocol will be followed according to the standard CIBMTR long-term follow-up mechanism. The treatment arms will be compared with a two-sided log-rank test stratified on risk status. Tests will be performed pair-wise at the .01667 level in order to maintain study-wide type I error at 0.05. PFS will be compared between treatment arms as a time to event analysis. A secondary analysis of PFS will be conducted using Cox regression, adjusting for demographic and baseline characteristics which are statistically

different between treatment arms ( $p < 0.1$ ). Additionally, discontinuation of lenalidomide maintenance will be considered as a time-varying covariate in the Cox regression model.

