2.8.1 Changes to the planned analyses

Clarifications from the BMT CTN 07LT protocol

The protocol specified that for the primary endpoint of PFS, deaths will be counted as failures no matter when they occur. This is clarified to note that deaths that occur prior to the end of 2018 will be counted as failures and deaths that occur after progression will use time to progression rather than time to death for the primary analysis. Deaths through the end of follow-up in December 2018 will be counted, but deaths that occur between the end of BMT CTN 07LT in December 2018 and the database closure for the analysis will not be counted.

The protocol specified that for some of the secondary outcomes, the analysis would be completed once all alive patients have been followed for 5-years post randomization on the BMT CTN 0702 protocol. This is clarified to note that the secondary outcomes will be analyzed at the same time as the primary analysis -- once all alive patients have been followed for 5-years post randomization on the BMT CTN 0702 protocol or the end of 2018.

The protocol specified that a Cox model would be used to analyze PFS data, but did not require that treatment group and risk strata be included in the model. These factors will be included in the models.

Supplemental analyses of EFS and OS have been added to incorporate a Cox model analysis adjusting for baseline risk factors for the 0702-enrolled population and to incorporate a Cox model investigating EFS, baseline risk factors, and discontinuation of lenalidomide among the population that initiated maintenance therapy. Additional cause-specific analyses will show the Cox model results for each component of EFS, with censoring at the time of the other components.

Additional supplemental landmark analyses of PFS, OS, and EFS have been added to explore these outcomes between those on long term lenalidomide and those not on long term lenalidomide.

3. Participant Characteristics and Compliance

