4.1 Analysis of the Primary Endpoint

The primary analysis of PFS will include all randomized subjects from the BMT CTN 0702 protocol, classified according to their randomized treatment allocation, irrespective of treatment received [intent-to-treat]. The time to this event is the time from randomization on the BMT CTN 0702 protocol to progression, initiation of non-protocol anti-myeloma therapy (this includes lenalidomide if the dose is above 15mg), or death from any cause reported on BMT CTN 0702, BMT CTN 07LT, or to the CIBMTR. Patients will be censored at loss to follow-up or end of 2018, whichever comes first. For those lost to follow-up, if loss occurred during 0702, censoring will occur at last myeloma evaluation before loss to follow-up. For those lost to follow-up on BMT CTN 07LT, censoring will occur at the last contact date reported on the study status follow-up form. For those who completed BMT CTN 0702 but did not enroll on 07LT, censoring will occur at the last evaluation of progression provided by the CIBMTR.

The treatment arms will be compared with a two-sided log-rank test stratified on risk status. Tests will be performed pair-wise at the 0.05/3 level to maintain type I error at 0.05 for this endpoint in this analysis. A Kaplan-Meier plot of PFS and 5-year estimates of PFS will be provided by treatment group.

A secondary analysis of PFS will be conducted using Cox regression, with treatment arm and risk strata as covariates, and adjusting for demographic and baseline characteristics which are statistically different between treatment arms (p<0.1) for covariates specified in section 3.1. Start time will be randomization on BMT CTN 0702.

In another secondary analysis of PFS, discontinuation of lenalidomide maintenance will be considered as a time-varying covariate in a separate Cox regression model for those who initiated lenalidomide; in this model, the outcome will be the time to progression or death from initiation of lenalidomide. Initiation of maintenance lenalidomide on BMT CTN 0702 will be the start time for this analysis. CIBMTR data will be used to determine whether participants who discontinued study lenalidomide also discontinued commercial lenalidomide. The limited interpretation will be noted for this analysis, since it will include non-randomized comparisons and there may be bias in who enrolled in BMT CTN 07LT.

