4.3 Supplemental Analyses

A supplemental analysis of OS will be included in which OS is analyzed using Cox regression, with treatment arm and risk strata as covariates, and will include demographic and baseline characteristics which are statistically different between treatment arms (p<0.1) for covariates specified in section 3.1. Start time will be randomization on BMT CTN 0702 and all participants randomized on 0702 will be included.

Supplemental analysis of EFS will be included.

- The first will analyze EFS using Cox regression, with treatment arm and risk strata as covariates, and will include demographic and baseline characteristics which are statistically different between treatment arms (p<0.1) for covariates specified in section 3.1. Start time will be randomization on BMT CTN 0702 and all participants randomized on 0702 will be included.
- The second will explore cause-specific hazards for each component of EFS. Cox models
 with treatment arm, risk strata, and demographic/baseline covariates as specified above
 will be used. Start time will be randomization on BMT CTN 0702 and all participants
 randomized on 0702 will be included. For each component, the other components of EFS
 will be considered censoring events.
- The third will analyze EFS using Cox regression in the subset of 0702 participants who initiated lenalidomide maintenance therapy. In this model, the outcome will be the time to

progression or death and the start time will be initiation of maintenance lenalidomide. Discontinuation of lenalidomide maintenance will be considered as a time-varying covariate. Treatment group, strata, and baseline covariates used in the first EFS regression analysis will also be included. The limited interpretation will be noted for this analysis, since it will include non-randomized comparisons and there may be bias in who enrolled in BMT CTN 07LT and continued on lenalidomide maintenance.

Supplemental landmark analyses will be included. The endpoints of PFS, OS, and EFS will be explored in the 0702-enrolled population who is alive four years post randomization (OS) or who is alive and progression- or event-free (for PFS and EFS respectively). A log rank test will compare each outcome for the groups determined by those who were taking lenalidomide at four years post randomization compared to those who were not. Kaplan meier estimates of each outcome at 5 years post randomization will be provided for each lenalidomide status group.

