Supplemental Exhibit 07LT-6B: Cause-specific Multivariate Cox Regression Analysis of the Components of Event-free Survival

Maximum Likelihood Estimates and Hazard Ratios: Event=Progression, Censoring Events=SPM, Death

	Cox model	Parameter		Hazard Rati	0
Covariate	Estimate	p-value	Point		
			Estimate	Confidence limit	Confidence limit
Auto/Auto treatment arm vs					
Auto/Maintenance arm ¹					
Auto/Auto treatment arm vs Auto/RVD					
arm ¹					
Auto/RVD treatment arm vs					
Auto/Maintenance arm ¹					
Risk strata—High risk vs					
Risk strata—Standard risk					
Permanent discontinuation of					
lenalidomide					
(other adjustment factor as needed)					
(other adjustment factor as needed)					
(other adjustment factor as needed)					

¹ P-values are compared to the 0.05/3 significance level.

Maximum Likelihood Estimates and Hazard Ratios: Event=SPM, Censoring Events=Progression, Death

	Cox model	Parameter		Hazard Rati	0
Covariate	Estimate	p-value	Point Estimate	Confidence limit	Confidence limit
Auto/Auto treatment arm vs Auto/Maintenance arm ¹					
Auto/Auto treatment arm vs Auto/RVD arm ¹					
Auto/RVD treatment arm vs Auto/Maintenance arm ¹					
Risk strata—High risk vs Risk strata—Standard risk					
Permanent discontinuation of lenalidomide					
(other adjustment factor as needed)					
(other adjustment factor as needed)	· ·				
(other adjustment factor as needed)					

¹ P-values are compared to the 0.05/3 significance level.

Maximum Likelihood Estimates and Hazard Ratios: Event=Death, Censoring Events=Progression, SPM

	Cox model	Parameter		Hazard Rati	0
Covariate	Estimate	p-value	Point		
			Estimate	Confidence limit	Confidence limit
Auto/Auto treatment arm vs Auto/Maintenance arm ¹					
Auto/Auto treatment arm vs Auto/RVD					
arm ¹					
Auto/RVD treatment arm vs					
Auto/Maintenance arm ¹					
Risk strata—High risk vs					
Risk strata—Standard risk					
Permanent discontinuation of					
lenalidomide					
(other adjustment factor as needed)					
(other adjustment factor as needed)					
(other adjustment factor as needed)					

¹ P-values are compared to the 0.05/3 significance level.

Figure: A forest plot for the hazard ratios and confidence intervals may also be provided.

Supplemental Exhibit 07LT-6C: Multivariate Cox Regression Analysis of Event-free Survival from Initiation of Lenalidomide

Maximum Likelihood Estimates and Hazard Ratios

[figure not shown]
	Cox model	Parameter		Hazard Rati	0
Covariate	Estimate	p-value	Point		

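### The p<0.1 imbalance gate chooses covariates by chance and cannot identify confounders in the lenalidomide-discontinuation Cox models (Exhibits 4B, 5B, 6C).

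*SAP*

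**What the plan says.** SAP 3.1 gives a closed list of seven candidates: gender, ethnicity, race, Karnofsky score, adjudicated response at 0702 entry (tested at two cut-points), age, and pre-0702 therapy. The admission rule, applied to everyone randomized on 0702, is "Factors with a significance level <0.1 based on a chi-square test of differences using all three treatment arms (not pairwise tested) will be included". It comes from Protocol 5.3 ("A secondary analysis of PFS will be conducted using Cox regression, adjusting for demographic and baseline characteristics which are statistically" different at p<0.1) and is repeated in SAP 4.1: "adjusting for demographic and baseline characteristics which are statistically different between treatment arms (p<0.1) for covariates specified in section 3.1".

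Two terms are exempt. SAP 2.8.1 notes that the protocol's Cox model "did not require that treatment group and risk strata be included in the model. These factors will be included in the models".

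The gate reaches well beyond the PFS arm comparison:
- The appendix notes apply it in Exhibits 07LT-4A and 4B and in Supplemental Exhibits 5A, 5B and 6A.
- For the EFS model from start of lenalidomide (6C), SAP 4.3 says "Treatment group, strata, and baseline covariates used in the first EFS regression analysis will also be included".
- For the cause-specific EFS models (6B), SAP 4.3 specifies Cox models "with treatment arm, risk strata, and demographic/baseline covariates as specified above". All three 6B shells nevertheless carry a row for "Permanent discontinuation of lenalidomide".

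SAP 4.1 qualifies the PFS discontinuation model: "The limited interpretation will be noted for this analysis, since it will include non-randomized comparisons and there may be bias in who enrolled". SAP 4.3 does the same for the EFS version. The OS version (5B) appears only in the appendix, and 4.3 neither describes nor caveats it.

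**The concern.** In Exhibits 4B, 5B and 6C the coefficient of interest is discontinuation of lenalidomide, which was not randomized. A baseline factor confounds that coefficient if it is related both to stopping and to outcome. The gate tests neither relation. It tests association with randomized arm, and does so in all 758 patients, whereas these models cover only those who started lenalidomide. A strong confounder and an irrelevant factor therefore have the same chance of entering.

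At stake is the discontinuation hazard ratio in three secondary or supplemental models. If one of the seven factors does drive both stopping and outcome, it will usually be missing from the model although the data are in hand.

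**Working it through.** **1. Figures in the plan.** The plan gives no figure for how the gate performs. Its inputs are consistent: 247 + 254 + 257 = 758, and 0.05/3 = 0.01667, as in Protocol 5.3.

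**2. How often the gate admits a factor.** Under randomization each single test gives p<0.1 with probability about 0.10. Simulation with arms of 247/254/257 gave 9.8-10.3% for prevalences of 10-50%. Response has two nested cut-points and enters with probability r = 0.169-0.183 (assumed prevalences). Treating the factors as independent:
- P(none enters) = (1 - r) × 0.9^6 = 0.831 × 0.531 = 0.442 down to 0.817 × 0.531 = 0.434.
- Expected number entering = 6 × 0.1 + r = 0.77-0.78.

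These are repeated-trial figures. In 0702 the selected set is already fixed by existing data, and the documents do not say what it is.

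**3. Effect on the discontinuation HR.** The documents give no factor effects, so every input here is an assumption: 600 initiators, PFS hazard 0.17/yr, discontinuation hazard 0.15/yr, follow-up 4-7 years, a 25% risk stratum with log HR 0.4, and a true discontinuation HR of 1.00. One factor with the same HR on PFS and on discontinuation is omitted (1,000-1,500 simulated trials per setting). Cells show the estimated HR and the share with p<0.05.

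| Factor HR | Prevalence 50% | 20% | 10% |
|---|---|---|---|
| 1.25 | 1.01, 5% | 1.01, 5% | 1.00, 5% |
| 1.5 | 1.05, 7% | 1.03, 6% | 1.02, 6% |
| 2 | 1.15, 21-22% | 1.10, 12% | 1.06, 8% |
| 3 (extreme) | 1.39, 78% | 1.26, 47% | 1.14, 17% |

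Three 50% factors omitted together give 1.05, 8% (each HR 1.25) and 1.14, 20% (each 1.5). Effects in opposite directions bias downward: 0.95 (1.5 and 0.67) and 0.86 (2 and 0.5). With the factors included, the HR is 0.99-1.00 and p<0.05 in 4-7%.

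A separate simulation applied the gate itself (650 starters, prevalence 30%, 150 trials per setting). With factor HRs of 2 on both PFS and discontinuation the HR was 1.143 under the gate, 1.154 unadjusted and 1.005 always adjusted. With 1.5 on both it was 1.044, 1.049 and 0.999.

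**4. Effect on arm comparisons.** Assumptions: true HR 0.75, hazard 0.20/yr, follow-up 5-8 years, two-sided level 0.05/3, 1,500 trials per setting. Power with the gate versus 12 forced terms:
- no prognostic factor: 58.8 vs 59.3%
- one at HR 1.25: 58.3 vs 59.3%
- one at HR 1.5: 56.0 vs 58.9%
- one at HR 2: 55.1 vs 60.1%
- three at HR 1.5: 54.3 vs 59.7%

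Type I error over 12,000 trials was 1.72% with the gate and 1.91% forced (Monte Carlo SE 0.12; nominal 1.67%).

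**5. Room for the full list.** The extra terms are gender 1, ethnicity 1, race 2, Karnofsky 1, response 1, age 1 and therapy 2, which makes 9, or up to 12 with missing-value categories. Arm (2) and risk stratum (1) bring the total to 12-15, plus 1 for discontinuation in the initiator models.
- OS: survival of 68-80% (Protocol 1.2) gives 758 × 0.20 = 152 to 758 × 0.32 = 243 deaths, or 12.6-20.2 per parameter with 12 terms. With 600 initiators (assumed), 120-192 deaths over 13 terms is 9.2-14.8. At the low end with all missing categories, 152/15 = 10.1 and 120/16 = 7.5.
- SPM: Protocol 1.3 supports 4.5% up to (9 + 10)/231. That is 758 × 0.045 = 34 to 758 × 19/231 = 62 events. Over 12 terms this is 2.8-5.2 per parameter, and over 3 terms (arm, risk) 11.4-20.8. These are upper bounds, because 6B censors at progression.
- Death without progression or SPM: not given. At an assumed 2-6% of 758 (15-45 events), 3 terms leave about 5-15 per parameter.

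**The case against.** The gate is pre-specified and never looks at outcome, so the arm comparisons keep their type I error. A reader might infer from the selection argument that the secondary PFS, OS and EFS arm comparisons are biased or invalid. The documents do not support that: arms were randomized, and arm and risk stratum are always in the model. The power gain from forcing terms is within simulation noise when no factor is prognostic (0.5 points, SE 0.5) or one has HR 1.25 (0.9 points, SE 0.6). Part of the larger gains may reflect the slightly higher type I error with forced terms. All of this stands.

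A reader might also infer that the discontinuation HRs will be materially biased. That is not shown either. No document identifies any of the seven as a confounder, and a single factor of ordinary strength moves the HR very little. SAP 4.1 and 4.3 already promise to note limited interpretation for the PFS and EFS versions. Stopping for toxicity or withdrawal arises after 0702 entry, and entry factors cannot remove that confounding. In simulation, when an equal unmeasured factor remained, forcing in the measured one removed only about half the shift (1.10 to 1.05 at factor HR 1.5; 1.29 to 1.15 at HR 2).

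Finally, SAP section 5 calls the shells illustrative, so the 5B and 6B mismatches are documentation gaps and add no weight to the argument about the gate.

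What the objection does not answer is that the initiator models have no confounder set of their own, and the rule that fills them cannot find one. A caveat does not replace adjustment for factors already collected and listed.

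**Conclusion.** The point holds as a low-cost improvement to secondary and supplemental analyses. The gate is unsuited to Exhibits 4B, 5B and 6C. That conclusion follows from the design and needs no assumed effect.

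The size of any resulting bias rests wholly on assumed factor effects. For one omitted factor it is at most 1.05 against a true 1.00 at factor HRs of 1.25-1.5, and 1.06-1.15 at HR 2 depending on prevalence. It is larger only for extreme factors or several acting in the same direction.

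In the arm comparisons the gate is valid, and replacing it is a matter of modest precision. The primary analysis is unaffected.

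**What to change.** 1. In Exhibits 4B, 5B and 6C, drop the gate. Always include arm, randomized risk stratum and all seven SAP 3.1 candidates, with age continuous and a single response cut-point. Fix the coding, including sparse categories and missing values, without reference to outcomes in a dated SAP version. SAP 2.4 shows that 0702 endpoints have already been tested, which is the reason to take the whole list rather than choose from it now. Record the change from Protocol 5.3 in SAP 2.8.1, which already did this for arm and risk stratum.
2. Preferably use the same fixed list in 4A, 5A, 6A and the 6B progression model, described as a small precision gain and not as the correction of an error.
3. In the two sparse 6B models (SPM; death without progression or SPM), use only arm and risk stratum, adding age if events allow.
4. Remove the discontinuation row from the 6B shells. SAP 4.3 does not list it. 6B also covers all randomized patients from randomization, including any who never started lenalidomide, for whom discontinuation is undefined.
5. Describe Exhibit 5B in SAP 4.3 and extend the non-randomized-comparison caveat to it. Keep that caveat for 4B and 6C.

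The cost is about 9-12 extra degrees of freedom and a documented departure from a protocol-stated rule. In simulation the SE of the log HR rose from 0.127-0.128 to 0.129 for discontinuation (about 360 events) and from 0.110 to 0.111 for an arm comparison (about 520 events).

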3.2 Participant Compliance

A table listing significant protocol deviations/violations will be provided separately for those who continued lenalidomide maintenance therapy and those who did not, by treatment group for participants enrolled on 07LT. Reasons for permanent withdrawal of lenalidomide maintenance therapy will be tabulated.

A consort diagram will be provided to illustrate BMT CTN 07LT accrual, disposition, and follow up.

4. Analysis Plan

4.1 Analysis of the Primary Endpoint

The primary analysis of PFS will include all randomized subjects from the BMT CTN 0702 protocol, classified according to their randomized treatment allocation, irrespective of treatment received [intent-to-treat]. The time to this event is the time from randomization on the BMT CTN 0702 protocol to progression, initiation of non-protocol anti-myeloma therapy (this includes lenalidomide if the dose is above 15mg), or death from any cause reported on BMT CTN 0702, BMT CTN 07LT, or to the CIBMTR. Patients will be censored at loss to follow-up or end of 2018, whichever comes first. For those lost to follow-up, if loss occurred during 0702, censoring will occur at last myeloma evaluation before loss to follow-up. For those lost to follow-up on BMT CTN 07LT, censoring will occur at the last contact date reported on the study status follow-up form. For those who completed BMT CTN 0702 but did not enroll on 07LT, censoring will occur at the last evaluation of progression provided by the CIBMTR.

The treatment arms will be compared with a two-sided log-rank test stratified on risk status. Tests will be performed pair-wise at the 0.05/3 level to maintain type I error at 0.05 for this endpoint in this analysis. A Kaplan-Meier plot of PFS and 5-year estimates of PFS will be provided by treatment group.

A secondary analysis of PFS will be conducted using Cox regression, with treatment arm and risk strata as covariates, and adjusting for demographic and baseline characteristics which are statistically different between treatment arms (p<0.1) for covariates specified in section 3.1. Start time will be randomization on BMT CTN 0702.

In another secondary analysis of PFS, discontinuation of lenalidomide maintenance will be considered as a time-varying covariate in a separate Cox regression model for those who initiated lenalidomide; in this model, the outcome will be the time to progression or death from initiation of lenalidomide. Initiation of maintenance lenalidomide on BMT CTN 0702 will be the start time for this analysis. CIBMTR data will be used to determine whether participants who discontinued study lenalidomide also discontinued commercial lenalidomide. The limited interpretation will be noted for this analysis, since it will include non-randomized comparisons and there may be bias in who enrolled in BMT CTN 07LT.

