2.2 Handling Missing Data

All participants who were randomized on the parent protocol BMT CTN 0702 will be included in the analysis for BMT CTN 07LT. Data for patients not enrolled on the long-term follow-up protocol will be included with two parts combined: 1) 0702 data until their end of participation on the BMT CTN 0702 protocol; 2) follow up data provided through the Center for International Blood and Marrow Transplant Research (CIBMTR).

For time-to-event variables, participants who have not had an event or competing risk event will be censored at the time data for the endpoint is no longer available. For Quality of Life analyses, participants will be excluded at a particular time point if they do not complete the surveys within a +/- 90-day window for the particular time point in the analysis.

The time of progression that was adjudicated on BMT CTN 0702 by the 0702 Endpoint Review Committee (ERC) will be used for participants who progressed on BMT CTN 0702. There is no adjudication of progression on BMT CTN 07LT, so progression will be determined by site-reported responses.

For the primary endpoint of PFS and the secondary endpoints of EFS, overall survival and cumulative incidence of SPM, and for tabulation of cause of death, data from the BMT CTN 0702, BMT CTN 07LT, and from the CIBMTR will be used.

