Comparison	N	Total Events	PRG or NPT	DTH	Stratified Log-rank (Abs(Z)) ¹	p- value ²
Auto/Auto to	247	XXX	XXX	XXX	X.X	0.XX
Auto/RVD	254	XXX	XXX	XXX		
Auto/Auto to	247	XXX	XXX	XXX	X.X	0.XX
Auto/Maintenance	257	XXX	XXX	XXX		
Auto/RVD to	254	XXX	XXX	XXX	X.X	0.XX
Auto/Maintenance	257	XXX	XXX	XXX		

¹Absolute value of the Z statistic is reported; does not indicate direction.

 $^{^2}$ P-values are compared to the α =0.05/3 level for statistical significance.

³Only the first event (clinical progression (PRG), non-protocol anti-myeloma therapy initiation (NPT), death) is counted.

Notes for primary analysis:

Analysis population: 0702-enrolled

Events:

- Clinical progression
- initiation of non-protocol antimyeloma therapy
- death

BMT CTN 0702 Endpoint Review Committee data will be used for events when available (in general, during the first 38 months of follow-up on 0702). CIBMTR data will be used.

Censoring:

the date of last myeloma data collected through 0702 or 07LT or from the CIBMTR

Testing:

• two-sided log-rank test stratified on risk status at randomization. Significance level for each pairwise test is 0.05/3.

Exhibit 07LT-4A: Multivariate Cox Regression Analysis of Progression-free Survival (Secondary Analysis of PFS) – 0702 baseline factors

Maximum Likelihood Estimates and Hazard Ratios

			Hazard Ration	0	
Covariate		Point	Lower	Upper	Model
		Estimate	Confidence	Confidence	Parameter
			Limit	Limit	Estimate
					p-value
Auto/Auto treatment arm					
vs Auto/Maintenance					
arm ¹					
Auto/Auto treatment arm					
vs Auto/RVD arm¹					
Auto/RVD treatment arm					
vs Auto/Maintenance					
arm ¹					
Risk strata—High risk vs					
Risk strata—Standard					
risk					
(other adjustment factor					
as needed)					
(other adjustment factor					
as needed)					
(other adjustment factor					
as needed)	0.05/0 : :6				

¹P-values are compared to the 0.05/3 significance level.

Figure: A forest plot for the hazard ratios and confidence intervals may also be provided.

Notes for this secondary analysis:

Model covariates:

- Treatment group
- Randomized risk strata
- Any of the factors in column 2 of the table in Section 3.1 that have a test for treatment group differences that is significant at the 0.1 level
- No interactions will be included.

- Analysis population is 0702 participants
- Time to PFS is calculated from randomization
- proc phreg in SAS, no model selection procedures

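### For lost patients, the primary PFS censoring dates in SAP 4.1 conflict with other SAP passages, and no passage says whether censoring at loss or later CIBMTR data governs

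*SAP*

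**What the plan says.** SAP 4.1 opens its censoring text with a general sentence, also found in Protocol 5.3: "Patients will be censored at loss to follow-up or end of 2018, whichever comes first". It then splits patients into three groups:

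- Lost during 0702: "For those lost to follow-up, if loss occurred during 0702, censoring will occur at last myeloma evaluation before loss to follow-up".
- Lost on 07LT: "For those lost to follow-up on BMT CTN 07LT, censoring will occur at the last contact date" on the study status form.
- Completed 0702 without joining 07LT: censored at the last CIBMTR evaluation of progression.

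The event definition in the same section ends with "death from any cause reported on BMT CTN 0702, BMT CTN 07LT, or to the CIBMTR". The list of sources may qualify all three event types or only death.

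Other SAP passages bear on the same dates and events:

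- Section 1.2.1 ends event-free time at last myeloma follow-up, through December 2018.
- Section 2.2 adds CIBMTR follow-up to the 0702 data of anyone not enrolled on 07LT. For PFS it says "data from the BMT CTN 0702, BMT CTN 07LT, and from the CIBMTR will be used". Patients without an event "will be censored at the time data for the endpoint is no longer available".
- Exhibit 07LT-3 sets the censoring date for all patients as "the date of last myeloma data collected through 0702 or 07LT or from the CIBMTR". It says CIBMTR data will be used, and for adjudication "BMT CTN 0702 Endpoint Review Committee data will be used for events when available".
- Section 2.8.1 counts deaths through December 2018 and makes no exception for loss.
- Section 4.2 censors OS at last contact from either CIBMTR or study data. EFS is censored at last contact with no source named for that date.
- Section 2.8 plans no sensitivity analyses.

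**The concern.** Two analysts following this SAP could build different primary-endpoint datasets for the same lost patients.

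One combination does harm. Suppose a progression, new therapy or death reported to the CIBMTR after loss counts as a failure, but a lost patient without such a report stays censored at the last evaluation before loss. The lost patients who stay in the risk set are then exactly those who go on to fail. Lost patients can add later failures but no later event-free time. Kaplan-Meier PFS is pulled down for a reason unrelated to treatment.

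For losses on 07LT the problem is different and smaller. Last contact need not include a myeloma assessment, so it can credit progression-free time that nobody checked.

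**Working it through.** **Passages side by side**

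| Source | Lost during 0702, no event | Lost on 07LT, no event |
|---|---|---|
| SAP 4.1 | last myeloma evaluation before loss | last contact |
| SAP 1.2.1 | last myeloma follow-up | last myeloma follow-up |
| SAP 2.2 | when endpoint data run out, CIBMTR data added | when endpoint data run out |
| Exhibit 07LT-3 | last myeloma data, any source | last myeloma data, any source |

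For 07LT losses, 4.1 differs from 1.2.1 and the exhibit whatever the CIBMTR holds. For 0702 losses, 4.1 differs from 2.2 and the exhibit only if the CIBMTR holds data after the loss; 1.2.1 does not clearly conflict there.

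For events after loss, 4.1 (sources), 2.2, 2.8.1 (deaths) and the exhibit point to counting them. The general censoring sentence in 4.1 points to not counting them. Nothing ranks the two.

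**Plan figures.** No stated figure depends on the censoring rule. The related ones reproduce: 0.05/3 = 0.01667; 758 × 0.55 = 416.9, or 417; 758 × 0.75 = 568.5, or 569.

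**Size for 0702 losses (simulation, 200,000 patients per scenario)**

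- From the documents: 3-year PFS of 55-75% (SAP 2.1), with 65% as the central value; median survival after progression of 29 or 48 months (Protocol 1.2); arm sizes from the SAP exhibits.
- Assumed: exponential PFS; 5-20% of PFS events are deaths without progression; visits every 3 or 6 months; administrative end at 5-8 years; 5 or 15% loss by year 4 (26-97 of 758 lost before an event); yearly CIBMTR evaluations for a covered fraction of lost patients.

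Bias in 5-year PFS, in percentage points, against complete follow-up:

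| CIBMTR coverage | All later events count, censor before loss | Only later deaths count, censor before loss |
|---|---|---|
| 100% | -0.6 to -2.4 | -0.1 to -1.4 |
| 50% | -0.3 to -1.4 | -0.1 to -0.9 |
| 25% | -0.2 to -0.9 | -0.1 to -0.7 |
| 10% | -0.1 to -0.6 | not tabulated |
| 0% | 0.0 to -0.5 | 0.0 to -0.5 |

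- Nothing counted after loss: 0.0 to -0.5 at any coverage. This is a visit-interval effect.
- Events and evaluations from any source: -0.2 to +0.3 at 50-100% coverage.
- Central case (65%, 15% loss, all later events): -2.1, -1.2, -0.6 and -0.2 at 100, 50, 25 and 0% coverage.

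A simpler check with exact progression dates gave -0.7 to -2.3 at 100% coverage and -0.4 to -1.3 at 50%. The any-source rule gave 0.0 to -0.1.

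**Yardstick.** Central 5-year PFS is 0.65^(5/3) = 0.488. For an arm of 254, ignoring censoring, SE = √(0.488 × 0.512 / 254) = 0.031, or 3.1 points.

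**Test level.** Log-rank rejection with no true difference: 247 vs 257 patients, unstratified, 8,000 trials per scenario, nominal 0.0167, Monte Carlo SE 0.0014.

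| Loss | Coverage | All events | Deaths only | Any source |
|---|---|---|---|---|
| 5% vs 15% | 100% | 0.023 | 0.017 | 0.017 |
| 5% vs 15% | 50% | 0.021 | 0.019 | 0.018 |
| 5% vs 15% | 25% | 0.017 | 0.016 | 0.018 |

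With equal loss of 10% or 15%, every rule gave 0.014-0.018.

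**Size for 07LT losses.** With regular visits and 2-8% loss per year after year 4, last contact and last evaluation differ by at most about 0.2 points. With assumed gaps of 6-24 months between the two dates and 5-20% of patients assigned a loss time in months 42-60, last contact raises 5-year PFS by 0.1 to 1.2 points.

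**The case against.** The strongest reply is that the passages can be harmonised. If lost means that no source holds further data, then 4.1, 2.2 and the exhibit agree for 0702 losses. This reading fits the 2.2 censoring sentence but is not secure. Section 4.1 ties loss to a particular study, and it grants CIBMTR evaluations expressly only to those who completed 0702 without joining 07LT. It also leaves the 07LT conflict in place. What stands is that the 0702 conflict is conditional on later CIBMTR data.

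A reader might infer that the SAP is silent on CIBMTR events after loss. It is not. Section 2.2 covers patients lost during 0702 because they are not enrolled on 07LT, and 4.1 and the exhibit also bring in CIBMTR data. What is missing is precedence over censoring at loss.

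It is also fair to say that the larger bias needs a mixed reading, with events from after loss and censoring from before it. No passage prescribes that mix outright, although 4.1 read literally produces it. Either rule applied consistently does little harm. With non-informative loss, using 6-24 months of later CIBMTR follow-up in full, rather than ignoring it, adds about 1 to 31 events among 758 patients and moves 5-year PFS by no more than 0.1 point.

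Section 5 calls the exhibit templates illustrative, so one could say that 4.1 simply governs. That would settle the 0702 censoring date, but not the tension inside 4.1 between its event sources and its general censoring sentence.

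**Conclusion.** The point holds as a conflict of rules on the primary endpoint that should be fixed. It is unconditional for 07LT losses and conditional on later CIBMTR data for 0702 losses. Precedence between censoring at loss and events reported afterwards is unstated.

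Under the mixed reading the 5-year PFS estimate is biased low by the amounts tabulated above, always by less than one arm's standard error. If nothing after loss counts, the bias is at most about 0.5 points. The 07LT effect is small, and its size depends on the assumed gap between last evaluation and last contact.

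Loss rates and CIBMTR coverage are assumptions; the documents give neither. The simulations take loss as non-informative and did not model adjudication.

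A reader might go further and infer that the pairwise tests are invalid. The results do not support that. The level stays near nominal with equal loss. The clearest excess, 0.023, needed 5% against 15% loss together with full coverage.

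**What to change.** Use one rule in SAP 1.2.1, 2.2, 4.1 and Exhibit 07LT-3:

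> The event is the first progression, start of non-protocol anti-myeloma therapy or death reported on 0702, on 07LT or to the CIBMTR through 31 December 2018, including after loss to follow-up on 0702 or 07LT. Patients without an event are censored at their latest myeloma evaluation from any of these sources through that date.

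- Leave the Endpoint Review Committee rule in 2.2 and Exhibit 07LT-3 as it is.
- In 4.2, state which censoring date and sources EFS uses. Leave OS unchanged.
- Add to the planned follow-up tables (Exhibit 07LT-1 and Supplemental Exhibit 07LT-1) the number lost by arm and how many of these have later CIBMTR data.

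The cost is SAP wording and reworked derivation code; section 2.5 already plans the CIBMTR retrieval. There are two downsides. More progressions will rest on unadjudicated CIBMTR reports. A small asymmetry also remains, because a death without a recent evaluation still counts while a survivor is censored at the last evaluation. This is included in the -0.2 to +0.3 points shown for the any-source rule.
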